## **Objective:**

The main purpose of this study is to observe hemodynamic effects of initiating sodium-glucose co-transporter 2 inhibitors (SGLT2i) in patients admitted to the intensive care unit with acute decompensated heart failure.

## **Study Purpose and Rationale:**

In 2008, the U.S. Food and Drug Administration (FDA) mandated new diabetes medications be tested for cardiovascular safety following the increase in heart failure hospitalizations seen with rosiglitazone in the RECORD trial (1). SGLT2i recently came onto the market, and accordingly multiple trials have assessed the cardiovascular safety of SGLT2i. These medications inhibit the sodium-glucose co-transporter 2 in the proximal tubule of the glomerulus, leading to reduced absorption, and increased excretion, of sodium and glucose (2). Not only were these medications found to be safe, but they have shown benefit in regards to cardiovascular outcomes.

First, the EMPA-REG OUTCOME trial reported a significant reduction in the primary composite outcome of myocardial infarction, stroke, and cardiovascular death, as well as a 35% reduction in heart failure (HF) hospitalization in patients randomized to empagliflozin, versus placebo, with established atherosclerotic cardiovascular disease (ASCVD) (3). The CANVAS trial then showed similar results with canagliflozin in a mixed cohort of patients with established, or risk factors for, ASCVD (4). The DECLARE-TIMI-58 trial showed reduced cardiovascular death or HF hospitalization in patients randomized to dapagliflozin versus placebo. Interestingly, this trial had a majority of enrolled patients with only risk factors for ASCVD, without established disease. Additionally, the reduction in HF hospitalization was seen in both patients with and without HF at baseline, of which only 10% of enrolled patients carried the diagnosis (5). The DAPA-HF trial demonstrated significantly less major adverse cardiac events in heart failure with reduced ejection fraction patients, regardless of underlying diabetes status (6). Also, in the EMPEROR-REDUCED trial, empagliflozin reduced the composite end point of heart failure hospitalization or cardiovascular death (7). Lastly, in the SOLOIST-WHF trial, sotagliflozin was shown to reduce the total number of deaths from cardiovascular causes and hospitalization and urgent visits for heart failure compared to placebo when initiated during a heart failure hospitalization, or within three days of discharge (21). Currently, dapagliflozin is FDA approved for use in patients with heart failure with reduced ejection fraction (HFrEF), regardless of diabetes status.

The proposed mechanism of reduction in heart failure hospitalization with SGLT2i is multi-factorial, with the most significant reason thought to be due to reduced plasma volume and neurohormonal activation via its natriuretic and osmotic diuretic effects (8). Additionally, animal models have suggested favorable effects on the sympathetic nervous system and sodium-hydrogen exchanger leading to reduced cardiac injury, hypertrophy, fibrosis, remodeling, and systolic dysfunction (9,10). Furthermore, increased ATP production, improved systolic function, and reduced cardiac work in non-diabetic mice with heart failure treated with empagliflozin, versus placebo, has been reported (11). In the updated 2021 Expert Consensus Decision Pathway for management of HFrEF, SGLT2i are recommended in patients on beta blockade and ARNI/ACE/ARB with EF  $\leq 40\%$ , NYHA Class II-IV HF, regardless of a diagnosis of diabetes (12).

Multiple trials, including DAPA-HF and EMPEROR-Reduced, have shown that SGLT2i have been beneficial in reducing risk of cardiovascular death or hospitalization for patients with HFrEF, but these studies were not conducted in hospitalized acutely decompensated patients requiring ICU admission and continuous hemodynamic monitoring. Similarly, SOLOIST-WHF demonstrated a reduction in the same end points, where an SGLT2i was initiated within three days after a hospitalization for a heart failure exacerbation. Therefore, SGLT2i initiation was not conducted in an acutely decompensated clinical setting. While SGLT2i are FDA approved for use in HFrEF population, there are limited data specifically addressing the role of SGLT2i in the acute setting in patients with acute decompensated heart failure, and even less data related to its use in the patients requiring ICU-level care. Given the limited data, the decision whether or not to use SGLT2i in this population is currently based on the individual physician's discretion. The exact mechanism of cardiovascular benefit continues to be the source of further research. We hypothesize that heart failure patients with acute decompensated heart failure will similarly benefit from the SGLT2i-associated natriuresis and diuresis. This mechanism should improve invasive hemodynamics during an inpatient ICU stay.

### **Study Design, Study Procedures, and Statistical Procedures**

This study is designed as a single center, prospective, randomized controlled study to assess cardiac benefit of SGLT2i in 40 consecutive patients (20 treatment, 20 control) admitted to University of Chicago Cardiac Intensive Care Unit (CCU) Advanced Heart Failure Service. Patients will be randomized to one of two routine care arms: treatment with an SGLT2i (dapagliflozin 10 mg daily) or no SGLT2i. Assuming a power of 80% and alpha of 0.05, 16 patients are needed in each arm of the study to detect a 5 mmHg change in pulmonary capillary wedge pressure (PCWP), and 18 patients are needed in each arm of the study to detect a 0.75 L/min/m^2 change in Fick cardiac index (CI).

Patients  $\geq 18$  years old, with heart failure with reduced ejection fraction (HFrEF), defined as left ventricular ejection fraction (LVEF)  $\leq 40\%$ , who are admitted to the CCU for acute decompensated heart failure and determined to need pulmonary artery catheter in place for continuous hemodynamic monitoring following right heart catheterization, will be included in this study. Patients listed for cardiac transplantation or on mechanical support will be excluded. Due to the inability to consent patients following sedation given during the right heart catheterization,

patients determined to have a high likelihood of needing CCU admission, based on individual clinical presentation, will be approached for recruitment and asked for informed, written consent. However, patients will only be enrolled if it is determined independently to admit the patient to the CCU with the pulmonary artery catheter in place. If determined to need CCU care with continuous pulmonary artery catheter monitoring, patients will then be randomized, in a 1:1 fashion using the random number generation function in Microsoft Excel, to either treatment with an SGLT2i (dapagliflozin 10mg once daily) or no SGLT2i. Therefore, we anticipate recruiting and consenting more than 40 patients, but we will only randomize and treat patients that fulfill all inclusion criteria. Patients consented but not meeting randomization criteria will not have any data collected or change to their management.

The patient's treating physician will be able to override randomization assignment if the physician determines that the assignment is not in the patient's best interest. These patients would be kept on study and their data would be used for observational research within this study.

Data points to be collected: Leveled invasive hemodynamics measured via pulmonary artery catheter at end expiration, standing weights, intake and outputs, blood glucose from basic metabolic panels (BMP) taken at those time points, HbA1C (if not within 3 months), blood pressure (cuff pressure), vasoactive doses, and renal function (measured by serum creatinine and estimated GFR) will be captured at multiple time points during CCU admission, as described below. All data points collected for use in this study are being measured as part of the patient's routine care.

**(1) Cardiac catheterization lab prior to CCU arrival:** Initial baseline hemodynamics obtained in the cardiac catheterization lab prior to CCU arrival will be collected.

- a) Cardiac index (L/min/m^2) by Indirect Fick Method
- b) Right atrial pressure (RAP) (mmHg)
- c) Pulmonary artery systolic pressure (PASP) (mmHg)
- d) Mean pulmonary artery pressure (mPA) (mmHg)
- e) Pulmonary artery diastolic pressure (PADP) (mmHg)
- f) Pulmonary capillary wedge pressure (PCWP) (mmHg)
- g) Pulmonary artery pulsatility index (PAPI)
- h) Right ventricular stroke work index (RVSWI) (mmHg L m^-2)
- i) Systemic vascular resistance (SVR) (dynes/sec/cm^5)
- j) Pulmonary vascular resistance (PVR) (dynes/sec/cm^5)
- k) Systolic, diastolic, and mean blood pressure (SBP/DBP/MAP) (mmHg)
- l) Aortic pulsatility index (API)

**(2) Hour 0 – Leveled hemodynamics,** repeated within two hours of arrival to CCU bed from cardiac catheterization lab prior to SGLT2i administration/equivalent if randomized to no SGLT2i arm, will be collected. All baseline data points to be collected at this time.

- a. Cardiac index (L/min/m^2)
- b. RAP (mmHg)
- c. PASP (mmHg)

- d. mPA (mmHg)
- e. PADP (mmHg)
- f. PCWP (mmHg)
- g. PAPi
- h. RSVWI (mmHg L m^-2)
- i. SVR (dynes/sec/cm^5)
- j. PVR (dynes/sec/cm^5)
- k. SBP/DBP/MAP
- l. API
- m. Standing weight
- n. Urine output
- o. Blood glucose taken from BMP
- p. HbA1c
- q. Current Vasoactive doses
- r. Renal function (serum Creatinine, serum eGFR)
- s. Total diuretic dose

(3) **Hour 1** – Following repeat hemodynamics in CCU bed, patients will be given SGLT2i if randomized to SGLT2i arm, or not given SGLT2i if randomized to no SGLT2i arm.

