### **Potential Risks**

SGLT2i have been shown to have beneficial effects on renal function (5,20). However, due to its direct effect on the kidneys, SGLT2i are labeled for patients with eGFR  $\geq 20\text{ml/min}/1.73\text{m}^2$  or GFR  $\geq 30\text{ml/min}/1.73\text{m}^2$  depending on the medication. Due to this, we will exclude patients with eGFR  $< 30\text{ml/min}/1.73\text{m}^2$ . Increased risk of genital mycotic infections (i.e. vaginitis and balanitis), urinary tract infections, pyelonephritis, urosepsis, and perineal necrotizing fasciitis have been reported, but only genital infections have been shown to be a significant risk in large randomized trials (3-5). Additionally, there has been a small increased risk of diabetic ketoacidosis associated with the use of SGLT2i, though this was predominantly in patients on insulin, who will not be included in this study (5). Lastly, canagliflozin was associated with an elevated risk of lower limb amputation and bone fractures compared to placebo in the CANVAS trial, but this was not seen with the CREEDANCE trial of canagliflozin, or in other SGLT2i randomized controlled trials, including the EMPA-REG OUTCOME, DECLARE-TIMI-58, DAPA-HF, EMPEROR-Reduced trials completed for empagliflozin and dapagliflozin (4). We will not be using canagliflozin in this study.

The adverse reactions of dapagliflozin in order of incidence include female genital mycotic infections, nasopharyngitis, urinary tract infection, back pain, increased urination, male genital mycotic infections, nausea, influenza, dyslipidemia, constipation, dysuria, pain in extremity, increase in creatinine, increase in hematocrit, dyslipidemia, hypersensitivity reactions, urosepsis, necrotizing fasciitis of the perineum.

Since patients are randomized to two routine care arms, we do not believe there is additional risk incurred by participating in this study. The treating physician will be notified of the randomization assignment and can override the assignment if they believe it to be in the best interest of the patient. While SGLT2 inhibitor therapy is approved for use in patients with HFrEF, there is not sufficient data guiding its use in the ICU-setting in patients with acute decompensated heart failure. If benefit is shown in the SGLT2i population, the arm without SGLT2i would lose the hypothesized benefit of renal and cardiovascular benefits during the CCU stay.

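### The treating physician can override the assignment once the arm is known, and nothing before randomisation asks whether both arms are acceptable, so foreseeable objections can become arm-dependent overrides

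*Combined protocol and SAP*

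**What the plan says.** Under Study Design, Study Procedures, and Statistical Procedures, the treating physician may "override randomization assignment if the physician determines that the assignment is not in the patient's best interest". Overridden patients stay on study and their data go to observational research within it. Potential Risks gives the order of events: "The treating physician will be notified of the randomization assignment and can override the assignment".

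Two conditions must be met before randomisation. The first is the clinical decision on admission: "patients will only be enrolled if it is determined independently to admit the patient to the CCU with the pulmonary artery catheter in place". The second is the set of eligibility criteria. Several of these remove patients for whom the drug might be objected to: low eGFR, type 1 diabetes, a history of DKA, insulin above a low-dose sliding scale, allergy or intolerance to the class, and pregnancy or breastfeeding. No criterion asks the treating physician whether either assignment would be acceptable.

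The planned size is "40 consecutive patients (20 treatment, 20 control"). It is set against 16 per arm for PCWP and 18 per arm for CI. The same section expects to consent more than 40 patients. The documents give no expected override rate, no allowance for overrides and no definition of the analysis population.

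**The concern.** A physician with a prior view on the drug will object to only one of the two assignments. If that view is first sought after the arm is known, the patient has already been randomised, and whether an override follows depends on the arm drawn.

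The documents give grounds for views in both directions. The rationale leaves SGLT2i use in this population to the individual physician. Potential Benefits cites guidelines that recommend the class in heart failure generally. Potential Risks says that data in the ICU setting are insufficient. The eligibility criteria deal with part of one direction (the drug is unsuitable) and with none of the other (the physician already wants it given).

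Two consequences are possible, depending on how overridden patients are analysed. Kept in their randomised arm, they dilute the treatment difference. Removed from the comparison, they are post-randomisation losses that differ by arm and are linked to clinical judgement, so the groups may no longer be comparable. With 20 per arm, a handful of patients matters in either case.

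**Working it through.** **Inputs.** From Study Design, Study Procedures, and Statistical Procedures:
- "Assuming a power of 80% and alpha of 0.05, 16 patients are needed in each arm" for a PCWP difference of 5 mmHg
- "18 patients are needed in each arm of the study to detect a 0.75 L/min/m"² difference in CI
- 20 per arm planned

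Alpha is taken as two-sided and applied to each primary outcome without adjustment; the plan does not state sidedness.

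**The plan's own figures.** No SD is given, so 16 and 18 cannot be reproduced independently. They can only be inverted. With a two-sample t-test at 80% power, the standardised difference is 1.024 at 16 per arm and 0.961 at 18 per arm:
- PCWP: SD = 5 / 1.024 = 4.88 mmHg
- CI: SD = 0.75 / 0.961 = 0.78 L/min/m²

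At 20 per arm with no overrides, power is 88.4% (PCWP) and 84.2% (CI).

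**Reading A: overridden patients analysed as randomised.** Assume each override is a full-effect crossover and the SD is unchanged. With *a* crossovers in one arm and *b* in the other, out of 20 each, the expected difference is multiplied by 1 − a/20 − b/20 = 1 − c/20, where c = a + b.

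| Crossovers among 40 (c) | Factor | PCWP power | CI power |
|---|---|---|---|
| 0 | 1.00 | 88.4% | 84.2% |
| 1 | 0.95 | 85.0% | 80.4% |
| 2 | 0.90 | 81.0% | 76.0% |
| 3 | 0.85 | 76.5% | 71.2% |
| 4 | 0.80 | 71.4% | 65.9% |

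The break-even point can be checked without the unstated SD. In the normal approximation, power at 20 per arm returns to 80% when the factor equals √(n required / 20), whatever the SD or sidedness:
- PCWP: √(16/20) = 0.894, so c = 20 × (1 − 0.894) = 2.1
- CI: √(18/20) = 0.949, so c = 20 × (1 − 0.949) = 1.03

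The t-test gives 2.2 and 1.1. CI therefore falls below 80% at the second crossover, and PCWP at the third.

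**Reading B: overridden patients left out of the comparison.** The difference is not diluted, but patients are lost.

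| Patients left out | PCWP power | CI power |
|---|---|---|
| 1 per arm (19 v 19) | 87% | 82% |
| 2 per arm (18 v 18) | 85% | 80% |
| 3, all from one arm (17 v 20) | 85.5% | 80.9% |
| 4, all from one arm (16 v 20) | 84.2% | 79.5% |

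Power holds up much better here. These figures say nothing about bias, which is the main harm on this reading and cannot be quantified from the documents.

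**With objections settled before the draw.** If patients not randomised are replaced from the consented pool and no overrides follow, power stays at 88.4% and 84.2%.

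**The case against.** The strongest reply is that the loss of power depends on facts the documents do not give. There is no override rate, and one override in 40 leaves both outcomes at or above 80% even as randomised. The dilution figures also need an as-randomised analysis, whereas sending these patients' data to observational research can be read as removing them from the comparison. Both points stand.

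Second, the eligibility criteria already screen out several foreseeable objections to the drug, both arms are described as routine care, and leaving the decision to the physician may reflect uncertainty more than strong preference. Hour 0 measurements also come before the first dose, so some overrides may rest on new information. This stands too: the documents do not show that overrides will be common, or that a prior check would prevent most of them. It does not answer the gap, since no criterion covers a physician who already wants the drug given.

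A reader might go further and infer that overrides will use up a margin the sponsor set aside for them. The documents do not support that. They never explain why 20 was chosen over 16 and 18, and they do not say how often overrides are expected.

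A reader might also conclude that the override itself should be narrowed. That is a matter of clinical management. It is not needed for the design aim, and the unrestricted override sits beside the statement in Potential Risks that participation adds no risk.

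**Conclusion.** The design gap is established by the text: the override follows disclosure of the arm, and no acceptability check precedes randomisation. Its consequence is conditional on an override rate that is not stated.

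Analysed as randomised, the tolerance is about 1 crossover among 40 for CI and about 2 for PCWP. These break-even counts assume full-effect crossover and an unchanged SD, but do not depend on what the SD is. The power percentages rest in addition on the back-solved SDs and a two-sided alpha of 0.05 per outcome. If overridden patients are left out, 2 lost per arm still leaves 85% (PCWP) and 80% (CI), and the concern becomes selective loss by arm. A check before the draw can reduce avoidable overrides under either reading, so it is worth having whichever analysis set is later defined. This is a cheap improvement to the design; it does not show that the trial is underpowered.

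**What to change.** Add one inclusion criterion, completed before the assignment is drawn: the treating physician confirms in writing that both dapagliflozin and no SGLT2i are acceptable for this patient. Patients without that confirmation are not randomised. Leave the physician's right to override unchanged, and record the time, direction and reason of every override so that its extent and pattern can be reported.

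The cost is one eligibility line, one check box and a short log. A few consented patients will not be randomised and accrual may be slightly slower, but the plan already expects to consent more than 40. The description of the sample as consecutive would need qualifying, and the results would apply to patients for whom both arms were judged acceptable.

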#### (4) **Hour 3**

- a. Cardiac index (L/min/m^2)
- b. RAP (mmHg)
- c. PASP (mmHg)
- d. mPA (mmHg)
- e. PADP (mmHg)
- f. PCWP (mmHg)
- g. PAPi
- h. RSVWI (mmHg L m^-2)
- i. SVR (dynes/sec/cm^5)
- j. PVR (dynes/sec/cm^5)
- k. SBP/DBP/MAP
- l. API
- m. Standing weight
- n. Urine output
- o. Blood glucose taken from BMP
- p. HbA1c
- q. Current Vasoactive doses
- r. Renal function (serum Creatinine, serum eGFR)
- s. Total diuretic dose

(5) **Hour 27** - 2 hours after 2nd dose of SGLT2i, which will be administered 24 hours after first dose, or equivalent time period after which the dose would have been given for the No-SGLT2i arm.

- a. Cardiac index (L/min/m^2)
- b. RAP (mmHg)
- c. PASP (mmHg)
- d. mPA (mmHg)
- e. PADP (mmHg)
- f. PCWP (mmHg)
- g. PAPi
- h. RVSWI (mmHg L m^-2)
- i. SVR (dynes/sec/cm^5)
- j. PVR (dynes/sec/cm^5)
- k. SBP/DBP/MAP
- l. API
- m. Standing weight
- n. Urine output
- o. Blood glucose taken from BMP
- p. HbA1c
- q. Current Vasoactive doses
- r. Renal function (serum Creatinine, serum eGFR)
- s. Total diuretic dose

**(6) Hour 51 & Hour 75 - if vasoactives are still required and pulmonary artery catheter is still being used for routine clinical care**, we will continue SGLT2i for up to 4 doses, and the additional invasive hemodynamics repeated two hours after each dose will be collected.

- a. Cardiac index (L/min/m^2)
- b. RAP (mmHg)
- c. PASP (mmHg)
- d. mPA (mmHg)
- e. PADP (mmHg)
- f. PCWP (mmHg)
- g. PAPi
- h. RVSWI (mmHg L m^-2)
- i. SVR (dynes/sec/cm^5)
- j. PVR (dynes/sec/cm^5)
- k. SBP/DBP/MAP
- l. API
- m. Standing weight
- n. Urine output
- o. Blood glucose taken from BMP
- p. HbA1c
- q. Current Vasoactive doses
- r. Renal function (serum Creatinine, serum eGFR)
- s. Total diuretic dose

Leveled invasive hemodynamic measurements, standing weights, intake and outputs, blood glucose, blood pressure, vasoactive doses, and renal function will stop being collected for the

study after the fourth dose of SGLT2i, or equivalent timing for those randomized to the No-SGLT2i arm.

The leveled hemodynamic measurements measured via a pulmonary artery catheter at end expiration will be collected. A picture will be taken and shown to an Advanced HF attending not involved with the patient's current care and blinded to treatment for interpretation.

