The patient's participation in the study will end after completion of 4 doses of the SGLT2i or sooner if patient is transferred out of the CCU and continuous hemodynamic monitoring is discontinued, or if patient develops any of the safety end points as listed below. The physician will discuss the ongoing treatment plan with the patient at this point.

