## **Outcomes**

Primary outcome: Change in Indirect Fick cardiac index and change in PCWP

Secondary outcomes: changes in pulmonary artery pulsatility index (PAPi), Right atrial pressure (RAP), pulmonary artery systolic pressure (PASP), mean pulmonary artery pressure (mPA), pulmonary artery diastolic pressure (PADP), right ventricular stroke work index (RWSWI), systemic vascular resistance (SVR), pulmonary vascular resistance (PVR), mean arterial pressure (MAP), renal function, 24 hour urine output, changes in weight, changes in vasoactive dose, and blood glucose levels

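### The plan names no primary analysis set, and does not say whether patients whose assignment is overridden enter the primary comparison or in which arm

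*Combined protocol and SAP*

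**What the plan says.** The section on Study Design, Study Procedures, and Statistical Procedures describes a randomised trial of 40 patients, 20 per arm: "patients will then be randomized, in a 1:1 fashion using the random number generation function in Microsoft Excel". The same section allows the treating physician to override the assignment when it is judged not to be in the patient's best interest. The next sentence is the only one on how overridden patients are handled: "These patients would be kept on study and their data would be used for observational research within this study".

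Potential Risks confirms that the decision is made with the allocation known: "treating physician will be notified of the randomization assignment and can override the assignment if they believe it to be in the best interest".

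The other places where an analysis set might be defined do not define one:
- The Objective reads "The main purpose of this study is to observe hemodynamic effects".
- Outcomes reads "Primary outcome: Change in Indirect Fick cardiac index and change in PCWP", with no population attached.
- The sample-size statement reads "Assuming a power of 80% and alpha of 0.05, 16 patients are needed in each arm" for a 5 mmHg change in PCWP. It asks for 18 per arm for a 0.75 L/min/m² change in cardiac index. It gives no standard deviation, test or allowance for overrides.

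**The concern.** Randomisation protects the comparison only if patients are compared in the groups to which they were allocated. An override happens after allocation, is made by someone who knows the allocation, and rests on a view of the patient's prospects. If overridden patients are dropped, or moved to the group whose treatment they received, that judgement shapes the two groups.

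The text leaves three readings open: set aside, as treated, or as randomised. Because the plan does not choose, the choice could be made after the data are seen. With 20 patients per arm, a few overrides are enough for the choice to matter, both for bias and for power.

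**Working it through.** **1. Is an analysis set named anywhere?** From the Objective to the References, no section mentions intention-to-treat, per-protocol, as-treated or any other analysis set. The design section says who is randomised and what happens to patients who consent but are not randomised. It does not say how a patient who is randomised and then overridden is analysed, or whether that patient counts towards the 40.

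**2. The plan's own figures.** The 16 and 18 per arm cannot be reproduced, because no standard deviation, test or sidedness is given. Solving backwards:
- Normal approximation, two-sided: n = 2(1.960 + 0.842)² SD²/δ². With SD 5 mmHg and δ = 5, n = 2 × 7.85 × 25/25 = 15.7, so 16. With SD 0.8 and δ = 0.75, n = 2 × 7.85 × 0.64/0.5625 = 17.9, so 18.
- Two-sided two-sample t-test at 80% power: SD 4.72 to 4.88 mmHg for PCWP and 0.757 to 0.780 L/min/m² for cardiac index. The range allows for rounding up.

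Both figures are therefore coherent, but only under assumed SDs. The steps below use 4.88 and 0.780.

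**3. Illustrative bias with no true effect.** All of these are assumptions: 20 per arm; the k patients with the worst prognosis are overridden, in the SGLT2i arm only; prognosis correlates r with the outcome; the test is a two-sided t-test. Let S be the expected sum of the k largest of 20 standard normal values.
- k = 2: S = 1.867 + 1.408 = 3.275.
- k = 4: S = 1.867 + 1.408 + 1.131 + 0.921 = 5.327.
- Shift if removed = |r| × SD × S/(20 − k).
- Shift if counted as treated = |r| × SD × [S/(20 − k) + S/(20 + k)].

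With |r| = 0.5 and SD 4.88, |r| × SD = 2.44 mmHg. Type I error is from simulation.

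| Analysis | k | PCWP shift (mmHg) | Type I error |
|---|---|---|---|
| Removed | 2 | 2.44 × 0.182 = 0.44 | about 6% |
| Removed | 4 | 2.44 × 0.333 = 0.81 | about 8% |
| As treated | 2 | 2.44 × (0.182 + 0.149) = 0.81 | about 8% |
| As treated | 4 | 2.44 × (0.333 + 0.222) = 1.35 | about 13% |
| As randomised | 2 or 4 | 0 | about 5% |

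At r = +0.5 (worse prognosis, worse change) the shift favours the drug. At r = −0.5 it is the same size against the drug. If the same kind of patient is overridden in both arms, the mean bias is close to zero.

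**4. Power cost of as-randomised analysis.** Assume full crossover with k overrides per arm. The mean difference becomes δ(1 − 2k/20). For k = 2 that is 0.8 × 5 = 4 mmHg and 0.8 × 0.75 = 0.60 L/min/m².

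| Scenario, 20 per arm randomised | PCWP power | CI power |
|---|---|---|
| No overrides | 88% | 84% |
| 2 per arm, as randomised | 68-71% | 63-66% |
| 2 per arm removed (18 v 18), unrelated to prognosis | 85% | 80% |

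The upper ends (71.4% and 65.9%) allow only for the diluted mean. The lower ends (68.1% and 62.8%) are simulated, and also carry the extra spread from mixing treatments within an arm.

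**The case against.** **Exclusion may seem to be what the sponsor means.** A reader might infer this from the word *observational*. The text does not support that as the settled or likelier reading. The same sentence keeps these patients on study and uses their data within it, the Objective describes the whole study as observing effects, and the schedule describes the arms by randomised assignment. Equally, keeping a patient on study shows that follow-up continues, not that the patient is analysed as randomised. The text is silent on the choice.

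**A false benefit may seem the natural result.** A reader might infer this by picturing the sickest patients being taken off the drug. The documents do not support a direction. The outcome is a change, so the sickest may improve least or, through regression to the mean, most. Larger figures can be produced: type I error reaches 21.6% as treated if 4 of 20 are overridden, all in the SGLT2i arm, chosen perfectly by prognosis, at correlation 0.7. Nothing in the plan points to that combination.

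**The sample size may seem to assume no overrides.** The plan does not say so. It needs 16 or 18 per arm and enrols 20. That margin could be an allowance for such losses, and only the sponsor can say.

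**The stakes are limited.** Data and Safety Monitoring calls this an initial pilot of 40 patients followed for less than 4 days, and overrides may prove rare. That stands, and it caps the severity. It does not remove the gap, because the trial is powered at 80% and the protocol provides for overrides in two places. Blinded reading of the tracings protects measurement, not the choice of who is compared.

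**Conclusion.** The point holds as an omission: the primary analysis set is not named, and the one sentence on overridden patients leaves three readings open. On two of them the comparison loses the protection of randomisation. That conclusion needs no figures.

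The bias figures are illustrations. They rest on assumed SDs, test, override counts, one-sided selection and correlation, and they can run either way or be near zero. The power figures rest on back-solved SDs and full crossover. This is a cheap improvement.

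**What to change.** Replace the sentence on the use of overridden patients' data with:

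> Patients whose assignment is overridden stay on study, count towards the 40, are not replaced, and are analysed in the arm to which they were randomised in the primary analysis. Their data are collected at the same scheduled hours (0, 3, 27 and, where the stated conditions hold, 51 and 75), timed from when the first dose was given or would have been given, whichever treatment they receive, subject to the end-of-participation rules. Overrides are reported by arm, with reason and timing. As-treated and override-excluded analyses are supportive only.

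The time anchor is needed because collection now stops after the fourth dose, or at the equivalent time for patients randomised to no SGLT2i. A patient randomised to SGLT2i and overridden off it fits neither case. The existing conditions stay in force: the later hours apply "if vasoactives are still required and pulmonary artery catheter is still being used for routine clinical care", and participation ends "sooner if patient is transferred out of the CCU and continuous hemodynamic monitoring is discontinued".

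In the sample-size statement, the sponsor should say what the 16 and 18 per arm assume about overrides, and whether the margin up to 20 is meant to cover them.

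The change needs no extra patients or procedures and leaves the physician's right to override as it is. The real cost is the power lost to dilution shown above. Patients with no later measurement would still need a missing-data rule.
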